comparisons, one-way analysis of variance (ANOVA) followed by Dunnett's test, where appropriate, was used to determine the statistical significance of the difference between means. The follow-up parametric data were compared using the paired student's t-test. Non-parametric data were determined by chi-squared tests. Analyses of primary and secondary outcomes are performed with the use of time-to-event methods according to the intention-to-treat principle. All analyses were two-sided, and $p<0.05$ was considered statistically significant. Statistical analyses were performed using Prism version 5 (GraphPad Software Inc., La Jolla, CA, USA).

5. Handling of Missing Data :

Omit the cases with missing data and analyze the remaining data.

2. Introduction and Rationale

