2.5 Regulatory

This study will be conducted in compliance with the protocol approved by the Institutional Review Board, and according to Good Clinical Practice standards. No deviation from the protocol will be implemented without the prior review and approval of the IRB except where

it may be necessary to eliminate an immediate hazard to a research subject. In such case, the deviation will be reported to the IRB as soon as possible.

3. Objectives and Endpoints

3.1 Study Objectives:

3.1.1 Primary objective:

To evaluate the benefit of high protein supplementation and core muscle rehabilitation and trunk NMES intervention in weaning from ventilator

3.1.2 Secondary objectives:

The impact of renal function and digestion status after high protein intake
The benefit in nutrition status and diaphragm weakness and the correlation to weaning status

3.1.3 Other exploratory objectives (if any):

1.2 Study endpoints:

3.2.1 Primary endpoint:

Weaning rate

(weaning success defined as weaning from ventilator for 5 consecutive days)

3.2.2 Secondary endpoints:

In hospital mortality, Length of mechanical ventilator usage,
Length of ICU stay and total length of hospitalization,
Serum albumin level improvement, Creatinine clearance rate

3.2.3 Other exploratory endpoints (if any):

4. Study Design

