5.3 Withdrawal criteria

1. Return to ICU for unstable vital sign or any necessity of surgery.
2. Patient refuse further intervention
3. Physicians judge the patients' condition are not suitable for further intervention.

10. Treatments

6.1.Treatment Administration

1. High protein diet:

The HP groups will maintain unchanged total daily caloric intake and increasing protein content to 1.5g/kg/day. The specific formulas were chosen for their different energy and protein requirement (mainly Nutri-Aid , or NU-PEP HN , according to patients' digestion, and may add Whey-Aid if necessary (above formula are available in CGMH currently)).

We will maintain the nutrition strategies for 21 days according to patients' weaning condition. Protein provision was not reduced in case of renal failure.

2. Core muscle rehabilitation:

Sitting on bedside with or without aids, for 30 minutes, twice per day, 5 days per week, for 3 weeks.

3. Neuromuscular electrical stimulation (NMES):

NMES was applied for 30 min, twice per day, 5 days per week, for 3 weeks, via surface rectangular electrodes. Electrodes were placed on back designed to activate latissimus dorsi and abdominal wall designed to activate the transversus abdominis and internal and external oblique muscles as previously McCaughey et al described ³⁷. Electrical muscle stimulation was performed by using a commercial stimulator (GEMORE, GM300E, Taipei, Taiwan) with biphasic waves at a simulation frequency of 30 Hz and pulse width of 400s, cycling 2s on and 4s off. Electrical muscle stimulation intensity was gradually increased until a visible muscle contraction was observed (median 60 mA [range 50–65 mA].

The subjects in the control group received similar electrode placement and intervention duration, except that the stimulator power was off.

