11.2 Planned Statistical methods of analysis

Categorical variables were expressed as count and percentage. Parametric data were expressed as mean \pm standard deviation (SD). A Student's t-test was used to compare parametric data. Fisher's exact test was used to compare non-parametric data. We used a receiver operating characteristic (ROC) curve to identify the optimal cut-off-value for the maximum multiplication of sensitivity and specificity. Logistic regression was used for multivariate analysis. Kaplan–Meier survival analysis was performed to assess weaning and survival outcomes. Statistical significance was set at a p-value < 0.05 . Statistical analyses were performed using GraphPad Prism version 8 (GraphPad Software, La Jolla, CA, USA) and IBM SPSS Statistics 26 (SPSS, Chicago, IL, USA).

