11.2.2 Safety analysis

Wilcoxon matched-pairs signed rank test was used to compare parametric data (difference of baseline and follow-up serum creatinine and creatinine clearance)

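### Section 11.2.2 gives creatinine and creatinine clearance only a within-patient test, and no sentence in the plan spells out a renal comparison between arms

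*Combined protocol and SAP*

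**What the plan says.** Section 11.2.2 (Safety analysis) reads: "Wilcoxon matched-pairs signed rank test was used to compare parametric data (difference of baseline and follow-up serum creatinine and creatinine clearance". It is the only place where a test is assigned to these two variables. It names no follow-up time.

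The rest of the statistical text is general:

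- Synopsis, Statistical methods, on repeated data: "The follow-up parametric data were compared using the paired" Student's t-test. This too is within-patient.
- The same paragraph offers one-way ANOVA and then Dunnett's test, which, "where appropriate, was used to determine the statistical significance of the difference between means". No endpoint is attached.
- The same paragraph adds: "Analyses of primary and secondary outcomes are performed with the use of time-to-event methods". No renal event is defined anywhere.
- Section 11.2: a Student's "t-test was used to compare parametric data". No endpoint or arm contrast is given.
- Section 11.2.1 lists the variables for the Mann-Whitney test: weaning rate and three durations. No renal variable is among them. Section 11.2.3 (Additional analysis) is marked not applicable.

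Renal function is nevertheless a stated question. Section 3.1.2 lists "The impact of renal function and digestion status after high protein intake" as a secondary objective, and Section 3.2.2 lists "Serum albumin level improvement, Creatinine clearance rate" among the secondary endpoints. Section 6.1 states: "Protein provision was not reduced in case of renal failure".

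**The concern.** A matched-pairs test asks whether patients in a group changed from baseline. The objective asks whether high protein changed renal function. In patients ventilated for more than 21 days, creatinine and its clearance may move over three weeks whatever the diet, for example through recovery, new illness or muscle loss. The randomised usual-care arm is there to remove that common movement, but the renal test in 11.2.2 does not use it as a comparator.

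A drift shared by all arms could therefore be credited to, or blamed on, the diet. This matters because protein stays at 1.5 g/kg/day even in renal failure, while the reassurance in Section 2.4 comes from preliminary work at 1.2 g/kg/day.

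**Working it through.** **Inputs from the documents.** Sections 4.1 and 11.1: 10 patients in usual care (arm 1) and 30 in each of three high-protein arms. Check: 10 + 3 × 30 = 100, the stated total. Section 4.2: 20% loss, with 100 and 80 as the two totals. If the loss is spread evenly (an assumption), 30 × 0.8 = 24 and 10 × 0.8 = 8. Two-sided 0.05 (Synopsis). The plan has no power calculation, SD or renal effect size to reproduce.

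**Assumptions.** Changes from baseline are normal with SD 1, so effects are in SDs of change. The same drift occurs in every arm and the diet has no effect. Drifts of 0.2 to 0.5 SD are shown as a range.

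**Step 1: the paired test under a common drift.** Approximate rejection rate = Φ(drift × √n − 1.96). For 0.3 SD and n = 30: 0.3 × 5.477 − 1.96 = −0.317, and Φ(−0.317) = 0.38. Simulating the signed-rank test itself (10,000 trials; figures can move by about a point between runs) gives these percentages of trials significant:

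| Common drift | n = 30 | n = 24 | n = 10 | n = 8 |
|---|---|---|---|---|
| 0.2 SD | 18% | 16% | 9% | 6% |
| 0.3 SD | 35% | 28% | 13% | 9% |
| 0.4 SD | 53% | 45% | 20% | 14% |
| 0.5 SD | 73% | 63% | 28% | 20% |

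**Step 2: the between-arm test under the same drift.** The drift cancels in the difference between arms. A Mann-Whitney test of change, arm 2 v arm 1, is significant in 4.8% of trials (30 v 10) and 4.5% (24 v 8).

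**Step 3: within-arm p-values set side by side.** The arms are independent, so P(arm 2 significant, usual care not) = p₂ × (1 − p₁). At 0.3 SD:

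- 30 v 10: 0.35 × 0.87 = 0.30
- 24 v 8: 0.28 × 0.91 = 0.25
- 30 v 30: 0.35 × 0.65 = 0.23

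The misleading pattern appears in nearly a quarter of trials even with equal arms. The 30 v 10 split adds about 7 points.

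**Step 4: precision of the between-arm estimate.** Half-width of the 95% interval = t(0.975, n₁ + n₂ − 2) × √(1/n₁ + 1/n₂) SD.

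- Arm 2 v arm 1, 30 v 10: 2.024 × 0.365 = 0.74
- Arm 2 v arm 1, 24 v 8: 2.042 × 0.408 = 0.83
- Arms 2–4 pooled v arm 1, 90 v 10: 1.984 × 0.333 = 0.66
- Pooled, 72 v 8: 1.991 × 0.373 = 0.74

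Power of the Mann-Whitney test at a true difference of 0.5 SD is about 24% (30 v 10) or 20% (24 v 8).

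**The case against.** The best defence is that a between-arm renal test is implied. Section 11.2.2 itself labels the renal values parametric, Section 11.2 gives parametric data a Student's t-test, and the synopsis gives group means ANOVA with Dunnett's test, which compares with a control. A reader might infer from 11.2.2 that the plan has no between-group method for such data at all. The documents do not support that stronger claim. But the general sentences do not settle whether the comparison is of final values or of change, at what time, or between which arms. Where the plan does name the renal variables, it chooses a paired test.

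Three further points stand and limit the concern:

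- The plan nowhere says that it will set within-arm p-values side by side, so Step 3 describes a possible misuse. Nor is the unequal allocation the root of that problem, though a reader might think so.
- A reader might also infer that the paired approach would hide a diet effect that offsets a usual-care trend. That is not shown. If usual care falls by an assumed 0.8 SD and arm 2 is flat, the paired test in arm 2 is significant in about 5% of trials. But the paired test in 10 usual-care patients is significant in about 58%, against about 53% for the between-arm test. The trend would be seen if usual care is reported too.
- The trial calls itself exploratory (Section 11.1), and individual patients are watched: creatinine at least twice weekly (Section 2.4), graded adverse events (Section 9.1), and withdrawal on a physician's judgement (Section 5.3). That protects patients, but it does not estimate the effect of the diet.

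**Conclusion.** The concern holds in a limited form: the renal analysis named in 11.2.2 is within-patient only, and no between-arm renal contrast is spelled out. Followed as written, it cannot attribute a renal change to high protein. How often this would mislead depends wholly on an unknown drift. Across the assumed 0.2 to 0.5 SD, the paired test in one high-protein arm is significant in about 18% to 73% of trials with no diet effect (16% to 63% after even 20% loss), against about 5% for a between-arm test. That shows how exposed the test is; it does not forecast that this trial's renal conclusion will be wrong.

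The gap should be closed, because it concerns a stated secondary objective and the safety of the diet. The primary weaning endpoint is not affected.

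**What to change.** In Section 11.2.2:

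- Make the renal analysis a between-arm comparison of creatinine and creatinine clearance at the end of the 21-day treatment period, naming the visit that supplies the value. Analyse change from baseline, or the final value adjusted for baseline.
- Report the difference with a 95% interval. Use arm 2 v arm 1 as the diet contrast. Give arms 2–4 pooled v arm 1 as a supporting estimate, noting that it mixes diet with rehabilitation and NMES.
- Keep the paired test as description within each arm.
- The plan omits cases with missing data, so state how many patients per arm lack the end-of-treatment value. Show an analysis using the last available value as a sensitivity analysis only, since it mixes times and may bring in values taken shortly before death.

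The cost is SAP wording and one table. Both variables are already followed weekly (Section 8), so no new patients or new types of measurement are needed. The price is imprecision, with the half-widths in Step 4. The text should say that the result is an estimate and that a non-significant difference does not establish renal safety.

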11.2.3 Additional analysis

Not applicable

11.2.4 The level of significance

A p-value less than 0.05 was considered significant and was denoted by * and p-value less than 0.01 was denoted by **.

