4.1 Overall Design

Research principles and methods

Patients

Patients (age \geq 20 years old) on mechanical ventilator for more than 21 days were recruited from

the respiratory care center (RCC). of Chang Gung Memorial Hospital in Taiwan.

The **inclusion criteria** were as follows:

1. age \geq 20 year old
2. using mechanical ventilator for more than 21 days (including patients under tracheostomy or endotracheal tube)
3. stable clinical condition, without using inotropic agent
4. maximal inspiratory pressure (MIP) $< 30\text{mmHg}$
5. under enteral nutrition (EN) via NG tube.

The **exclusion criteria** were as follows:

1. Acute infection and sepsis (fever up to 38.5 degree)
2. Severe neuromuscular disease, or uncontrolled epilepsy
3. Bony fracture or DVT history
4. Wound over the abdomen
5. Congestive heart failure with EF $< 40\%$ or using pacemaker
6. $\text{BMI} > 35 \text{ kg/M}^2$, or severe edema
7. Patients with hepatic failure, rapid progressed malignancy, or pregnancy were also excluded.
8. Under parenteral nutrition (PN)
9. Use pacemaker

Patient's identification will be recorded as a study code, which will not be mentioned in the publication.

[figure not shown]
Study Protocol

Patients will be randomly assigned into four groups: (1) Usual care (UC), (2) UC + high protein diet (HP), (3) UC + HP + core muscle rehabilitation, (4) UC + HP + core muscle rehabilitation + neuromuscular electric stimulation (NMES). Ten patients will be assigned to UC group. Thirty patients will be included in another 3 group. Before subject recruitment, sequential sealed envelopes were prepared by an independent investigator ([name]), with one chosen randomly by another investigator for each subject. The subjects were then assigned to each group according to the label in the envelope. The total daily caloric intake is based on the suggestion of nutritionist. The HP groups will maintain unchanged total daily caloric intake and increasing protein content to 1.5g/kg/day. The specific formulas were chosen for their different energy and

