11.1 Sample size Determination

This is an exploratory research, we determine the enrolled number according to the

number of patients admitted to RCC annually.

Ten patients will be assigned to UC group.

Thirty patients will be included in another 3 group.

A total 100 patients will be enrolled.

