11.2.1 Efficacy analysis

Kaplan–Meier survival analysis was performed to assess weaning and survival outcomes.

Mann Whitney test was used for compare non-parametric data (weaning rate, length of ventilator use, length of ICU stay and length of hospitalization).

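### No error control covers the primary endpoint, weaning rate, across four arms: the false-positive chance is roughly 5% to 21%, depending on a test and a set of comparisons that the plan does not fix

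*Combined protocol and SAP*

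**What the plan says.** Section 4.1: "Patients will be randomly assigned into four groups", namely usual care, then protein, rehabilitation and NMES added one at a time. Section 11.1 gives the sizes: "Ten patients will be assigned to UC group", "Thirty patients will be included in another 3 group" and "A total 100 patients will be enrolled". The same section calls the study exploratory and bases its size on annual admissions, without an effect size or power.

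The primary endpoint is weaning rate (section 3.2.1), a proportion. The documents describe its analysis in several ways:

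- Section 11.2.1: "Mann Whitney test was used for compare non-parametric data", with weaning rate first in the list of variables that follows. Kaplan-Meier analysis is also named.
- Section 11.2: Fisher's exact test for data it calls non-parametric, Student's t-test for parametric data, logistic regression for multivariate analysis, and Kaplan-Meier for weaning.
- Synopsis, Statistical Methods: for group "comparisons, one-way analysis of variance (ANOVA) followed by Dunnett's test, where appropriate", restricted to differences between means. Chi-squared tests are named for non-parametric data, and time-to-event methods for primary and secondary outcomes. "All analyses were two-sided".

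On significance, section 11.2.4 says "A p-value less than 0.05 was considered significant and was denoted by" an asterisk, with a second mark below 0.01. Section 11 does not say which arms are compared with which.

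**The concern.** A two-sample test applied to four arms has to be run more than once, and there are six possible pairs. If each result is judged at 0.05, the chance that at least one weaning comparison is flagged when nothing works exceeds 5%. A single starred pair could then be read as evidence at the 5% level when it is not.

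The plan already accepts error control across arms for means, yet leaves it off the endpoint that matters most. Dunnett's test also covers only comparisons with the control arm. The added value of rehabilitation over protein, or of NMES over rehabilitation, therefore has no error-controlled test even for means.

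**Working it through.** **Inputs from the documents.** Four arms; two-sided 0.05 per test; sizes 10 + 3 × 30 = 100, which reproduces the stated total and confirms that thirty means thirty per experimental arm.

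**Assumptions, because the documents are silent.** A common weaning rate of 30% to 70% in all arms (no true effect), and three candidate sets of comparisons:

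- each experimental arm against usual care (3 tests)
- adjacent add-on steps, 2 v 1, 3 v 2 and 4 v 3 (3 tests)
- all pairs (4 × 3 / 2 = 6 tests)

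**Step 1: independence benchmark.** 1 − (1 − 0.05)^m gives 1 − 0.95³ = 14.3% for three tests and 1 − 0.95⁶ = 26.5% for six. Comparisons that share an arm are correlated, so these values are too high. Two contrasts with usual care, for instance, have correlation (1/10) / (1/10 + 1/30) = 0.75.

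**Step 2: normal theory with the real allocation.** Take z = (x_i − x_j) / √(1/n_i + 1/n_j), with n = 10/30/30/30, and count trials in which any |z| exceeds 1.96 (2,000,000 simulated trials). The result is 10.4% for three contrasts with usual care, 13.3% for three add-on steps and 19.8% for six pairs. With four equal arms, the studentized range gives 20.3% for six pairs.

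**Step 3: binary weaning data with the tests named in the documents.** 400,000 simulated trials at each of 30, 40, 50, 60 and 70% weaning. Entries are the chance of at least one p<0.05.

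| Test | 3 v usual care | 3 add-on steps | 6 pairs |
|---|---|---|---|
| Mann-Whitney (11.2.1) | 9.9-11.4% | 12.6-14.0% | 18.8-21.0% |
| Pairwise chi-squared | 10.3-11.4% | 13.0-14.0% | 19.2-21.0% |
| Fisher's exact (11.2) | 5.1-6.4% | 7.0-7.4% | 10.9-11.8% |

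A single four-group chi-squared test, one possible reading of the synopsis, gives 4.8-4.9%. A separate simulation of the Mann-Whitney row put the lower end for the add-on steps at 12.5%.

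**Step 4: what control would require.** Bonferroni, or the first Holm step, for three contrasts uses 0.05 / 3 = 0.0167. A Dunnett-type bound for three contrasts with usual care at 10/30/30/30 is z = 2.28, a nominal p of about 0.023. For all six pairs the bound is z = 2.56, a nominal p of about 0.0105. With the first Holm step on the add-on contrasts, the simulated family error was 3.8-4.2%.

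**Step 5: price in power.** At an assumed 40/50/60/70% weaning across the four arms, Holm gives about 27% power to find any contrast with usual care and about 13% to find any add-on step.

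**The case against.** The strongest reply is that section 11.1 calls the trial exploratory and makes no power claim. Unadjusted p-values are common in such work, and strict family-wise control is partly a matter of preference. That stands as a reason for moderate severity. It does not close the point, because the plan still declares a primary endpoint and still calls p<0.05 significant. If p-values are only descriptive, the plan should say so.

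Second, the documents do not commit to a procedure with high error. The synopsis chi-squared could be one four-group test, a comparison of four Kaplan-Meier curves could also be one test, and Fisher's exact test is conservative at these sizes. This also stands, and it is why a range is given. But section 11.2.1 is the text specific to efficacy and it points to the high rows of the table, and no test comparing four curves is named.

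A reader might infer that the false-positive rate is simply about 20%. The documents do not support that as a flat statement: it needs all six pairs and Mann-Whitney or pairwise chi-squared, and no section says that six pairs will be tested. Dunnett's test and the synopsis's split into experimental and control groups suggest three contrasts with usual care.

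A reader might also multiply the seven listed endpoints by six pairs. That fails too. Section 11.2.2 analyses creatinine clearance by a paired test within patients, and serum albumin, if summarised as a mean, falls under ANOVA and Dunnett.

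**Conclusion.** The gap is real: nothing in the plan controls error across arms for weaning rate, and the efficacy section names a two-sample test for it. Under Mann-Whitney the chance of a false significant difference is about two to four times the nominal 5%: 10-11%, 12.5-14% or 19-21% for the three sets of comparisons. Fisher's exact test brings it to about 5-12%. Only a single overall test keeps it near 5% whatever pairs are of interest, and that protects only against the case where all four arms are equal.

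The figures assume 10/30/30/30 patients, equal weaning of 30-70% in every arm and one analysis of weaning. Running Kaplan-Meier comparisons or logistic regression as well would add to them. Because the study is declared exploratory, this is a change that should be made rather than a fatal flaw.

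**What to change.** In section 11.2.4, extend to weaning the control that the synopsis already applies to means. Before data are seen, the sponsor names one weaning test and one family of three contrasts, either each arm against usual care or the three add-on steps, and applies Holm or a Dunnett-type adjustment (the latter fits the contrasts with usual care). The section should also state that all other p-values are nominal and exploratory, carry no significance stars and are shown with 95% confidence intervals. Sections 11.2 and 11.2.1 and the synopsis should then name the same weaning test.

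The choice of family is the sponsor's. The add-on steps isolate each component but give up a claim for the full combination against usual care, although the stated aim concerns combined treatment. Contrasts with usual care keep that claim but do not test rehabilitation or NMES separately.

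The cost is wording only, with no added patients, visits or data. The downside is the stricter first step (p<0.0167 under Holm) and the low power shown above, about 27% or about 13% at 40/50/60/70% weaning. If the sponsor prefers not to adjust, the alternative is to label every weaning p-value nominal and make no claim of significance.
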